7.1.2.6.2 End of Treatment and Follow-up Tumor Imaging

In participants who discontinue study treatment, tumor imaging should be performed at the time of treatment discontinuation (±4-week window). If previous imaging was obtained within 4 weeks prior to the date of discontinuation, then imaging at treatment discontinuation is not mandatory. In participants who discontinue study treatment due to documented disease progression and the Investigator elects not to implement iRECIST, this is the final required tumor imaging.

In participants who discontinue study treatment without documented disease progression, every effort should be made to continue monitoring their disease status by tumor imaging using the same imaging schedule used while on treatment (every 12 weeks in Year 1 or every 12 weeks after Year 1) to monitor disease status until the start of a new anticancer treatment, disease progression, pregnancy, death, withdrawal of consent, or the end of the study, whichever occurs first.

7.1.2.6.3 RECIST 1.1 Assessment of Disease

RECIST 1.1 will be used as the primary measure for assessment of tumor response, date of disease progression, and as a basis for all protocol guidelines related to disease status (eg, discontinuation of study treatment). Although RECIST 1.1 references a maximum of 5 target lesions in total and 2 per organ, the Sponsor allows a maximum of 10 target lesions in total and 5 per organ, if clinically relevant to enable a broader sampling of tumor burden.

7.1.2.6.4 iRECIST Assessment of Disease

iRECIST is based on RECIST 1.1, but adapted to account for the unique tumor response seen with immunotherapeutic drugs. When clinically stable, participants should not be discontinued until progression is confirmed by the Investigator, working with local radiology, according to the rules below. This allowance to continue treatment despite initial radiologic PD takes into account the observation that some participants can have a transient tumor flare in the first few months after the start of immunotherapy, and then experience subsequent disease response.

A description of the adaptations and iRECIST process is provided in Appendix 4, with additional detail in the iRECIST publication ⁵⁰. iRECIST will be used by the Investigator to assess tumor response or progression, and make treatment decisions to remove or continue on protocol.

[figure not shown]
Table 5 Imaging and Treatment after First Radiologic Evidence of Progressive Disease

	Clinically Stable		Clinically Unstable	
	Imaging	Treatment	Imaging	Treatment
First radiologic evidence of PD by RECIST 1.1	Repeat imaging at 4 to 8 weeks to confirm PD.	May continue study treatment at the Investigator's discretion while awaiting confirmatory tumor imaging by site by iRECIST.	Repeat imaging at 4 to 8 weeks to confirm PD per Investigator's discretion only.	Discontinue treatment
Repeat tumor imaging confirms PD (iCPD) by iRECIST per Investigator assessment	No additional imaging required.	Discontinue treatment (exception is possible upon consultation with Sponsor).	No additional imaging required.	Not applicable
Repeat tumor imaging shows iUPD by iRECIST per Investigator assessment	Repeat imaging at 4 to 8 weeks to confirm PD. May occur at next regularly scheduled imaging visit.	Continue study treatment at the Investigator's discretion.	Repeat imaging at 4 to 8 weeks to confirm PD per Investigator's discretion only.	Discontinue treatment
Repeat tumor imaging shows iSD, iPR, or iCR by iRECIST per Investigator assessment.	Continue regularly scheduled imaging assessments.	Continue study treatment at the Investigator's discretion.	Continue regularly scheduled imaging assessments.	May restart study treatment if condition has improved and/or clinically stable per Investigator's discretion. Next tumor image should occur according to the regular imaging schedule.

iCPD = iRECIST confirmed progressive disease; iCR = iRECIST complete response; iRECIST = modified Response Evaluation Criteria in Solid Tumors 1.1 for immune-based therapeutics; iSD = iRECIST stable disease; iUPD = iRECIST unconfirmed progressive disease; PD = progressive disease; RECIST 1.1 = Response Evaluation Criteria in Solid Tumors 1.1..

HCC 18-087

Figure 1: Imaging and Treatment for Clinically Stable Participants after First Radiologic Evidence of PD Assessed by the Investigator

7.1.2.7 Tumor Tissue Collection and Correlative Studies Blood Sampling

Sample collection

Blood: Up to 30 cc of blood will be collected serially, in conjunction with IP washes, at catheter placement and removal, during interval cytoreduction (if performed at the discretion of the treating physician), and at each point where the intraperitoneal catheter is accessed for IP infusion (as further detailed below).

Peritoneal cells and fluid: Peritoneal cells and fluid will be collected through the IP catheter during catheter flushes, necessary to maintain patency. Collection will occur at catheter placement and removal, and each time the catheter is accessed for IP infusion.

At each time point we will collect, whenever present, any spontaneously outflowing liquid (*IP fluid*). We will also perform a "peritoneal wash", by injecting through the catheter 50 cc of sterile saline, followed by collection of the "peritoneal wash" fluid (*IP wash*, average of 8 cc expected). The dilution factor of the harvested cells (and soluble factors) in the IP wash or IP fluid will be evaluated by measuring the albumin concentration.

We will collect IP wash/fluid at days 1, 2, and 3 of cycles 1-6.

Tumor tissue: Tumor biopsy (typically obtained laparoscopically) will be collected at baseline (at catheter insertion) and again after four treatment cycles, and at time of IP port removal if feasible. The primary tumor biopsy site will be marked by a surgical clip so it can be assessed by biopsy at subsequent laparoscopic surgery.

7.1.3 Laboratory Procedures/Assessments

Details regarding specific laboratory procedures/assessments to be performed in this trial are provided below.

Laboratory tests for hematology, chemistry, urinalysis, and others are specified in Table 6.

Table 6 Laboratory Tests

Hematology	Chemistry	Urinalysis	Other
Hematocrit	Albumin	Blood	Serum β-human chorionic gonadotropin†
Hemoglobin	Alkaline phosphatase	Glucose	(β-hCG)†
Platelet count	Alanine aminotransferase (ALT)	Protein	PT (INR)
WBC (total and differential)	Aspartate aminotransferase (AST)	Specific gravity	aPTT
Red Blood Cell Count	Lactate dehydrogenase (LDH)	Microscopic exam (If abnormal)	Total thriiodothyronine (T3)
Absolute Neutrophil Count	Carbon Dioxide ‡	results are noted	T4
Absolute Lymphocyte Count	(CO ₂ or biocarbonate)	Urine pregnancy test †	Thyroid stimulating hormone (TSH)
	Uric Acid		
	Calcium		
	Chloride		Blood for correlative studies
	Glucose		
	Phosphorus		
	Potassium		
	Sodium		
	Magnesium		
	Total Bilirubin		
	Direct Bilirubin (If total bilirubin is elevated above the upper limit of normal)		
	Total protein		
	Blood Urea Nitrogen		
	Creatinine		
	CA-125		

[†] Perform on women of childbearing potential only. If urine pregnancy results cannot be confirmed as negative, a serum pregnancy test will be required.

[‡] If considered standard of care in your region.

HCC 18-087 57

Laboratory tests for screening should be performed within 28 days prior to the first dose of treatment. After Cycle 1, pre-dose laboratory procedures can be conducted up to 72 hours prior to dosing. Results must be reviewed by the investigator or qualified designee and found to be acceptable prior to each dose of trial treatment.

7.1.4 Other Procedures

7.1.4.1 Withdrawal/Discontinuation

When a participant discontinues/withdraws prior to trial completion, all applicable activities scheduled for the final trial visit should be performed at the time of discontinuation. Any adverse events which are present at the time of discontinuation/withdrawal should be followed in accordance with the safety requirements outlined in Section 7.2 - Assessing and Recording Adverse Events. After discontinuing treatment following assessment of CR, these participants should return to the site for a Safety Follow-up Visit (described in Section 7.1.5.3.1) and then proceed to the Follow-Up Period of the study (described in Section 7.1.5.3.2).

7.1.4.2 Blinding/Unblinding

Unblinded

7.1.5 Visit Requirements

Visit requirements are outlined in Section 6.0 - Trial Flow Chart. Specific procedure-related details are provided above in Section 7.1 - Trial Procedures.

7.1.5.1 Screening

Patients will be screened by the research staff with approval by PI.

7.1.5.2 Treatment Period

After placement of IP port and start of cycle 1 Day 1 until removal at 31 weeks.

7.1.5.3 Post-Treatment Visits

7.1.5.3.1 Safety Follow-Up Visit

The mandatory Safety Follow-Up Visit should be conducted approximately 4-6 weeks after the last dose of study treatment or before the initiation of a new anti-cancer treatment, whichever comes first. All AEs that occur prior to the Safety Follow-Up Visit should be recorded. Participants with an AE of Grade > 1 will be followed until the resolution of the AE to Grade 0-1 or until the beginning of a new anti-cancer therapy, whichever occurs first. SAEs that occur within 90 days of the end of treatment or before initiation of a new anti-cancer treatment should also be followed and recorded.

58

7.1.5.3.2 Follow-up Visits

Version Dated 5-20-2021

Participants who discontinue study treatment for a reason other than disease progression will move into the Follow-Up Phase and should be assessed every 12 weeks (84 \pm 14 days) by radiologic imaging to monitor disease status. Every effort should be made to collect information regarding disease status until the start of new anti-cancer therapy, disease progression, death, end of the study. Information regarding post-study anti-cancer treatment will be collected if new treatment is initiated.

7.1.5.3.3 Survival Follow-up

Participants who experience confirmed disease progression or start a new anticancer therapy, will move into the Survival Follow-Up Phase and will be obtained from the medical record or contacted by telephone every 12 weeks (+/- 4 weeks) to assess for survival status until death, withdrawal of consent, or the end of the trial, whichever occurs first.

7.2 **Assessing and Recording Adverse Events**

An adverse event is defined as any untoward medical occurrence in a patient or clinical investigation participant administered a pharmaceutical product and which does not necessarily have to have a causal relationship with this treatment. An adverse event can therefore be any unfavorable and unintended sign (including an abnormal laboratory finding, for example), symptom, or disease temporally associated with the use of a medicinal product or protocol-specified procedure, whether or not considered related to the medicinal product or protocol-specified procedure. Any worsening (i.e., any clinically significant adverse change in frequency and/or intensity) of a preexisting condition that is temporally associated with the use of the Merck's product, is also an adverse event.

Changes resulting from normal growth and development that do not vary significantly in frequency or severity from expected levels are not to be considered adverse events. Examples of this may include, but are not limited to, teething, typical crying in infants and children and onset of menses or menopause occurring at a physiologically appropriate time.

Merck product includes any pharmaceutical product, biological product, device, diagnostic agent or protocol-specified procedure, whether investigational (including placebo or active comparator medication) or marketed, manufactured by, licensed by, provided by or distributed by Merck for human use.

Adverse events may occur during the course of the use of Merck product in clinical trials, or as prescribed in clinical practice, from overdose (whether accidental or intentional), from abuse and from withdrawal.

All AEs, SAEs and other reportable safety events that occur after the consent form is signed but before treatment allocation/randomization must be reported by the investigator if the participant is receiving placebo run-in or other run-in treatment, if the event cause the

59

participant to be excluded from the study, or is the result of a protocol-specified intervention, including but not limited to washout or discontinuation of usual therapy, diet, or a procedure.

- All AEs from the time of treatment allocation/randomization through 30 days following cessation of study treatment must be collected by the investigator.
- All AEs meeting serious criteria, from the time of treatment allocation/randomization through 90 days following cessation of study treatment, or 30 days following cessation of study treatment if the participant initiates new anticancer therapy, whichever is earlier must be recorded by the investigator.
- All pregnancies and exposure during breastfeeding, from the time of treatment allocation/randomization through 120 days following cessation of study treatment, or 30 days following cessation of study treatment if the participant initiates new anticancer therapy must be reported by the investigator.
- Additionally, any SAE brought to the attention of an investigator at any time outside of the time period specified above must be reported immediately by the investigator if the event is considered to be drug-related.

Investigators are not obligated to actively seek AE or SAE or other reportable safety events in former study participants. However, if the investigator learns of any SAE, including a death, at any time after a participant has been discharged from the study, and he/she considers the event to be reasonably related to the study treatment or study participation, the investigator must promptly notify Merck.

7.2.1 Definition of an Overdose for This Protocol and Reporting of Overdose to the **Sponsor and to Merck**

For purposes of this study, an overdose of pembrolizumab will be defined as any dose of 1,000 mg or greater (≥5 times the indicated dose). No specific information is available on the treatment of overdose of pembrolizumab. In the event of overdose, the participant should be observed closely for signs of toxicity. Appropriate supportive treatment should be provided if clinically indicated.

If an adverse event(s) is associated with ("results from") the overdose of a Merck product, the adverse event(s) is reported as a serious adverse event, even if no other seriousness criteria are met.

If a dose of Merck's product meeting the protocol definition of overdose is taken without any associated clinical symptoms or abnormal laboratory results, the overdose is reported as a nonserious Event of Clinical Interest (ECI), using the terminology "accidental or intentional overdose without adverse effect."

All reports of overdose with and without an adverse event must be reported within 24 hours to the Sponsor and within 2 working days to Merck Global Safety. (Attn: Worldwide Product Safety; [contact])

HCC 18-087 60

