AEs associated with pembrolizumab exposure may represent an immunologic etiology. These immune-related AEs (irAEs) may occur shortly after the first dose or several months after the last dose of pembrolizumab treatment and may affect more than on body system simultaneously. Therefore, early recognition and initiation of treatment is critical to reduce complications. Based on existing clinical study data, most irAEs were reversible and could be managed with interruptions of pembrolizumab, administration of corticosteroids and/or other supportive care. For suspected irAEs, ensure adequate evaluation to confirm etiology or exclude other causes. Additional procedures or tests such as bronchoscopy, endoscopy, skin biopsy may be included as part of the evaluation. Based on the severity of irAEs, withhold or permanently discontinue pembrolizumab and administer corticosteroids. Dose modification and toxicity management guidelines for irAEs associated with pembrolizumab are provided in Table 3.

Table 3 Dose modification and toxicity management guidelines for immune-related AEs associated with pembrolizumab

General instructions:

- 1. Severe and life-threatening irAEs should be treated with IV corticosteroids followed by oral steroids. Other immunosuppressive treatment should begin if the irAEs are not controlled by corticosteroids.
- 2. Study intervention must be permanently discontinued if the irAE does not resolve or the corticosteroid dose is not ≤10 mg/day within 12 weeks of the last study intervention treatment.
- 3. The corticosteroid taper should begin when the irAE is \leq Grade 1 and continue at least 4 weeks.
- 4. If study intervention has been withheld, study intervention may resume after the irAE decreased to ≤ Grade 1 after corticosteroid taper.

irAEs	Toxicity Grade (CTCAE v5.0)	Action With Pembrolizumab	Corticosteroid and/or Other Therapies	Monitoring and Follow-up
	Grade 2	Withhold	• Administer corticosteroids (initial dose of 1 to 2 mg/kg prednisone or equivalent)	Monitor participants for signs and symptoms of pneumonitis
Pneumonitis	Recurrent Grade 2, Grade 3 or 4	Permanently discontinue	 followed by taper Add prophylactic antibiotics for opportunistic infections 	Evaluate participants with suspected pneumonitis with radiographic imaging and initiate corticosteroid treatment

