7.2.3.2 Events of Clinical Interest

Version Dated 5-20-2021

Selected non-serious and serious adverse events are also known as Events of Clinical Interest (ECI) and must be reported within 2 working days to Merck Global Safety. (Attn: Worldwide Product Safety; [contact]).

For the time period beginning when the consent form is signed until treatment allocation/randomization, any ECI, or follow up to an ECI, that occurs to any participant must be reported within 2 working days to Merck Global Safety if it causes the participant to be excluded from the trial, or is the result of a protocol-specified intervention, including but not limited to washout or discontinuation of usual therapy, diet, placebo treatment or a procedure.

For the time period beginning at treatment allocation/randomization through 90 days following cessation of treatment, or 30 days following cessation of treatment if the participant initiates

new anticancer therapy, whichever is earlier, any ECI, or follow up to an ECI, whether or not related to Merck product, must be reported within 2 working days to Merck Global Safety.

Events of clinical interest for this trial include:

- 1. an overdose of Merck product, as defined in Section 7.2.1 Definition of an Overdose for This Protocol and Reporting of Overdose to the Sponsor, that is not associated with clinical symptoms or abnormal laboratory results.
- 2. an elevated AST or ALT lab value that is greater than or equal to 3X the upper limit of normal and an elevated total bilirubin lab value that is greater than or equal to 2X the upper limit of normal and, at the same time, an alkaline phosphatase lab value that is less than 2X the upper limit of normal, as determined by way of protocol-specified laboratory testing or unscheduled laboratory testing.*

*Note: These criteria are based upon available regulatory guidance documents. The purpose of the criteria is to specify a threshold of abnormal hepatic tests that may require an additional evaluation for an underlying etiology.

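### The adverse-event collection windows disagree between sections, and late-onset non-serious immune-related events may go uncollected

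*Combined protocol and SAP*

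**What the plan says.** The window for ordinary adverse events is set in three places, and they differ.

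- **Section 7.2:** "All AEs from the time of treatment allocation/randomization through 30 days following cessation of study treatment must be collected by the investigator". Events that meet serious criteria are recorded "through 90 days following cessation of study treatment, or 30 days following cessation of study treatment if the participant initiates new anticancer therapy"; the first of these limits to be reached applies. Drug-related serious events that come to the investigator's attention are reportable at any time. Investigators have no duty to look for events in former participants.
- **Section 7.1.5.3.1:** "All AEs that occur prior to the Safety Follow-Up Visit should be recorded". That visit falls "approximately 4-6 weeks after the last dose of study treatment", or sooner if another anticancer treatment begins. Section 7.1.1.5.3 calls the same visit a 30-day visit.
- **Section 7.1.2.1:** AEs are recorded during the study and into follow-up, with no day limit. The same section takes assessment times from the flow chart and refers to 7.2 for detail.

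In the flow chart (section 6.1) the last AE mark is at the Safety Follow-up column. There is none at week 31 (catheter removal) or in survival follow-up.

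Section 7.2.3.2 gives events of clinical interest (ECIs) the same 90-day limit, again cut to 30 days by new anticancer therapy. It lists two: an overdose without symptoms, and a transaminase-plus-bilirubin laboratory pattern.

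Section 5.2.2 says that immune-related AEs (irAEs) "may occur shortly after the first dose or several months after the last dose of pembrolizumab treatment". Section 3.2 places monitoring of pneumonitis, colitis, hepatitis, endocrinopathies and nephritis under the secondary safety objective. Section 8 defines no irAE frequency, window or denominator.

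**The concern.** The protocol expects that some irAEs may begin well after dosing ends, yet the 90-day limit applies only to serious events and to two narrowly defined ECIs. Table 3 contains Grade 2 events that lead to withholding pembrolizumab and giving corticosteroids. Such an event need not meet serious criteria. If it starts in the second or third month after the last dose, no section clearly requires it to be recorded.

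What is at stake is the cumulative irAE frequency that this trial would report for a combination whose safety information section 7.1 itself describes as lacking. An uncollected event can only lower that frequency. Because the sections disagree, two patients with the same event on the same day could also be handled differently.

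**Working it through.** The documents state no irAE rate, so there is no planned figure to reproduce. The check has three parts.

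**1. Does any section require collection of a non-serious irAE at week 8 (day 56) after the last dose?**

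| Source | Reaches | Covers day 56? |
|---|---|---|
| 7.2, all AEs | day 30 | no |
| 7.1.5.3.1, up to the visit | about day 28 to 42 | no |
| 7.1.2.1, follow-up wording | no limit given | in words yes, but no AE assessment is scheduled |
| Flow chart, AE row | 4-6 week visit | no |
| 7.2 serious events; 7.2.3.2 ECIs | day 90 (or 30) | only if serious, or the hepatic pattern |
| 7.1.5.3.2 and 7.1.5.3.3 | 12-weekly | disease and survival status, not AEs |

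A Safety Follow-Up visit on day 28 does not end the 30-day duty in 7.2, so for ordinary AEs the two rules together give a cut-off between about day 30 and day 42. Section 5.5.1 points the same way: after day 30, concomitant medication is recorded only for serious events and ECIs. Flow chart footnote H takes patients off study at catheter removal or, if the catheter stays in, after the day 3 wash of the last cycle.

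**2. Calendar arithmetic.** The flow chart has cycle 1 at week 2 and cycle 6 at week 22.

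- Day 30 after the last cycle: 22 + 30/7 = week 26.3. Day 42: 22 + 42/7 = week 28. Day 90: 22 + 90/7 = week 34.9.
- Share of the 90 post-treatment days covered: 30/90 = 33%; 42/90 = 47%.
- Share of the whole span from week 2 to day 90, which is (22 − 2) × 7 + 90 = 230 days: (140 + 30)/230 = 74%; (140 + 42)/230 = 79%.
- Catheter removal at week 31 is (31 − 22) × 7 = 63 days after the last cycle. Section 2.1 instead puts removal 12 weeks after the last treatment, that is 84 days. Neither reaches day 90.

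**3. Illustration of size (assumptions, not document figures).** Assume a constant hazard of first non-serious irAE over the 230 days and a true cumulative frequency p by day 90. The recorded frequency is 1 − (1 − p)^(d/230), with d = 170 or 182 days, and the number missed is 45 × (p − recorded).

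| True p | Recorded, day-30 cut-off | Missed of 45 | Recorded, day-42 cut-off | Missed of 45 |
|---|---|---|---|---|
| 10% | 7.5% | 1.1 | 8.0% | 0.9 |
| 20% | 15.2% | 2.2 | 16.2% | 1.7 |
| 30% | 23.2% | 3.1 | 24.6% | 2.4 |
| 50% | 40.1% | 4.5 | 42.2% | 3.5 |

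Alternatively, assume directly that a share L of affected patients has onset after the cut-off; the recorded value is p(1 − L). For p = 20% and L from 5% to 30%, it runs from 19.0% to 14.0% (0.45 to 2.7 of 45 patients missed). For p = 30%, it runs from 28.5% to 21.0% (0.7 to 4.1 missed).

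**The case against.** The strongest reply is that section 7.1.2.1 already extends recording into follow-up, so a late event is not excluded. The wording is there, and for that reason a reader who infers that AEs are collected for 30 days and no longer goes too far. But the section takes its assessment times from a flow chart whose AE row stops at the 4-6 week visit, and it defers to 7.2. It adds a third window and does not settle which one governs.

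Second, tiering follow-up by seriousness is an ordinary design choice, and the more consequential late events are covered. Serious irAEs run to day 90, important medical events can count as serious, and drug-related serious events are reportable at any time. This stands and confines the point to non-serious events.

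Third, a reader might infer that two-thirds of the risk period is unobserved, since 60 of the 90 post-treatment days lie beyond day 30. That counts only the tail. Section 5.2.2 says these events may also come soon after the first dose, and a 30-day cut-off covers 74% of the span from week 2 to day 90.

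Fourth, a reader might infer that a planned irAE rate is biased, or that safety monitoring is compromised. Section 8 defines no such rate, and the suspension rule rests on dose-limiting toxicities in cycle 1, which late events cannot reach. Neither inference is supported.

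**Conclusion.** The point holds as an inconsistency with a practical consequence. Three AE windows must be reconciled, and under the operative ones a non-serious irAE with onset after about day 30 to 42 may be missed in any cumulative irAE frequency reported under the secondary safety objective. The direction is known: toward apparent safety.

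The size cannot be derived from the documents. The illustrations suggest anything from less than one to about four or five of 45 patients, depending wholly on the assumed frequency and onset pattern. They should not be cited as an estimate of bias. They also take day 90 as the end of the risk period; events after that would still be missed. Collection of serious irAEs, the cycle-1 suspension rule and the primary response endpoint are unaffected.

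**What to change.** - State one AE window, in days from last treatment, in sections 7.1.2.1, 7.1.5.3.1 and 7.2 and in the flow chart. Align the visit name in 7.1.1.5.3 with it.
- In 7.2, collect AEs in the Table 3 irAE categories through 90 days after last treatment as ordinary AE recording. Adding them to the ECI list is less suitable: it would bring reporting within 2 working days even for events through which Table 3 continues treatment, and the ECI window drops to 30 days once new anticancer therapy starts.
- Use the port-removal visit together with the 12-week follow-up contact or chart review, and add AE marks to the flow chart. Port removal alone is not enough, because it falls at day 63 or 84. A contact or chart check on or after day 90 should look back over the interval since the last AE assessment.
- Make footnote H and the former-participant clause in 7.2 consistent with this window.
- In section 8, define the irAE summary (grades, denominator, 90-day window) and show separately the patients who began new anticancer therapy before day 90.

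The cost is amendment wording and some extra AE recording up to day 90. No new procedure is needed, and treatment does not change.
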